45 (VCO_2) are recorded.
46

47 Steady-State Exercise

48 After the fourth muscle biopsy volunteers will complete 80-min of steady-state exercise on the cycle
49 ergometer at $60 \pm 5\%$ of their $VO_{2\text{peak}}$. During exercise VO_2 and VCO_2 will be measured for 4-min using a
50 metabolic cart (Parvo Medics) at approximately 0, 15, 30, 45, 60, and 75-min to determine substrate
51 oxidation. HR (measured continuously; Polar Electro) will be recorded at the same times as the metabolic
52

1 cart measurements. Breath samples will be collected at approximately 0, 20, 40, 50, 60, 65, 70, 75, and 80-
 2 min to determine exogenous carbohydrate oxidation using single-patient breath collection bags (Quin-Tron
 3 Instrument Company, Milwaukee, WI, USA). Breath will be transferred to 20 mL evacuated tubes.
 4

5 **Carbohydrate Supplementation**

6 After the post glycogen depletion muscle biopsy, volunteers will drink a CHO (glucose and fructose in a 2:1
 7 ratio) or CON beverage (Combat Feeding, Natick, MA). Carbohydrate will be provided at $1 \text{ g} \cdot \text{kg}^{-1} \cdot \text{hr}^{-1}$ in
 8 accordance with current American College of Sports Medicine Guidelines (40). The CON beverage will be
 9 sugar free and void of other nutrients to allow for assessment of the independent effect of carbohydrate
 10 availability on skeletal muscle and circulating microRNA expression. Beverages will be consumed
 11 immediately following the post glycogen depletion muscle biopsy and then every 30 min thereafter (5
 12 times) until the 3-hr post glycogen depletion muscle biopsy.
 13

14 Additionally, all participants will consume the CHO beverage at $1.8 \text{ g} \cdot \text{min}^{-1}$ during steady-state exercise to
 15 examine the impact of glycogen availability on exogenous carbohydrate oxidation efficiency. Volunteers
 16 will consume the beverage immediately before the start of the exercise and then again at 20, 40, and 60-
 17 min during the exercise bout. The CHO beverage consumed during exercise will be enriched with 200 mg
 18 of U- ^{13}C -glucose and U- $^{13}\text{C}_6$ -D-fructose (Cambridge Isotope Laboratory, Andover, MA, USA) to significantly
 19 increase the isotopic enrichment above natural levels and optimize the measurement of exogenous
 20 carbohydrate oxidation.
 21

22 **B5.4 Data Collection**

23 **Blood Sampling**

24 Blood samples will be collected using intravenous access by a USARIEM credentialed phlebotomist on

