 25 glycogen protocol days at baseline (before glycogen depletion), immediately following and every 30 min
 26 after the glycogen depletion protocol to assess circulating glucose and insulin (**Figure 1**). Baseline and 24-
 27 hr post glycogen depletion blood sampling will occur after a 10-hr overnight fast. A total of 120 mL of blood
 28 will be sampled from each volunteer during each glycogen depletion protocol day study (**Table 2**). Blood
 29 samples will be used to assess nutrient status (glucose and insulin) and circulating microRNA.
 30

31 Biochemical indices of metabolic homeostasis will be measured from stored samples at USARIEM.
 32 Unused serum will be retained for future use if subject provide permission in the informed consent
 33 document. Samples will be stored at USARIEM using subject identification numbers.
 34

35 **Table 2. Volume of Blood Sampled for Glycogen Protocol Day**

Tube	Number of Tubes	Total Volume (mL)
10 mL Red Top Tube	5	50
7 mL Red Top Tube	10	70
Total	15	120

37 **Breath Sample Processing for Isotopic Enrichment**

38 Measurement of $^{13}\text{C}/^{12}\text{C}$ in expired CO_2 will be measured using isotope-ratio mass and cavity ring-down
 39 spectroscopy (Metabolic Solutions, Inc., Nashua, NH).
 40

41 **Calculations of Carbohydrate and Fat Oxidation**

42 Fat and CHO oxidation will be calculated from VO_2 and VCO_2 measured using open circuit indirect
 43 calorimetry (4 min collection), neglecting the contribution of protein oxidation to the energy yield (44):
 44

45
$$\text{Fat oxidation (g/min)} = 1.695 \times \text{VO}_2 \text{ (L/min)} - 1.701 \times \text{VCO}_2 \text{ (L/min)}$$

1 Glucose oxidation (g/min) = $4.585 \times VCO_2 \text{ (L/min)} - 3.226 \times VO_2 \text{ (L/min)}$

2

3 *Calculations of Exogenous and Endogenous Glucose Oxidation*

4 Exogenous glucose oxidation can be calculated:

5

6 Exogenous glucose (g/min) = $VCO_2 \times [(Rexp - Rref)/(Rexo - Rref)]/k$

7

8 where VCO_2 is in L/min, $Rexp$ is the observed isotopic composition of expired CO_2 , $Rref$ is the isotopic
9 composition of expired CO_2 at rest before ingestion of the first dose of ^{13}C -glucose and U- $^{13}C_6$ -D-fructose,
10 $Rexo$ is the isotopic composition of the exogenous glucose ingested, and k (0.747 L/g) is the volume of
11 CO_2 provided by the complete oxidation of glucose. Endogenous glucose oxidation can be calculated by

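### The exogenous-oxidation formula takes its divisor from the ingested glucose, but the drink holds two labelled sugars 2:1 and nothing in the plan gives them equal enrichment

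*Combined protocol and SAP*

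**What the plan says.** B5.3, Carbohydrate Supplementation, specifies that after glycogen depletion "volunteers will drink a CHO (glucose and fructose in a 2:1" ratio, or the control beverage. For the next-day ride, "all participants will consume the CHO beverage at" 1.8 g/min, in servings just before the start and at 20, 40 and 60 min. On labelling it says: "The CHO beverage consumed during exercise will be enriched with 200 mg" of uniformly labelled glucose and fructose. It does not say whether 200 mg is the amount of each tracer or of both together, how it is divided, or whether it applies per serving or per bout. The Study Design text in B5.3 also says that both sugars are labelled, without an amount.

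B5.4, Calculations of Exogenous and Endogenous Glucose Oxidation, computes exogenous glucose as VCO2 × [(Rexp − Rref)/(Rexo − Rref)]/k. Rexo "is the isotopic composition of the exogenous glucose ingested". In the same sentence Rref, the resting breath background, is defined by reference to both labelled sugars. Endogenous oxidation is total carbohydrate oxidation minus this exogenous figure.

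The isotope measurements described in B5.4 are on expired CO2 only. No section says that the drink itself will be assayed.

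**The concern.** Labelled CO2 in breath comes from both sugars. Two separate problems can follow.

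- **Divisor.** If Rexo is the enrichment of glucose alone, the formula converts breath label to grams correctly only when fructose has the same enrichment.
- **Weighting.** Even if Rexo describes the whole drink, unequal enrichment makes a gram of one sugar count for more than a gram of the other. The result is then not total exogenous carbohydrate unless the sugars are oxidised in the proportion ingested.

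At stake is Objective 2 (B4), exogenous carbohydrate efficiency. Endogenous oxidation takes on the same error in g/min with the opposite sign. A wrong divisor can be recalculated later if tracer and sugar masses, or the drink's enrichment, were recorded. Unequal weighting cannot be undone, because breath 13CO2 does not show which sugar it came from.

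**Working it through.** **Inputs from the documents.** Formula and k from B5.4; 2:1 sugars, 1.8 g/min, 200 mg and four servings from B5.3 (Carbohydrate Supplementation); duration from B5.3 (Steady-State Exercise): "80-min of steady-state exercise on the cycle" ergometer. **Not given:** the tracer split, its basis, and any enrichment value. Splits below are assumptions.

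**1. The plan's constant.** The plan states "and k (0.747 L/g) is the volume of" CO2 from complete oxidation. Check: 6 × 22.4 / 180 = 0.747 L/g, which reproduces. Glucose and fructose have the same formula, so k suits both. The problem lies only in Rexo.

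**2. Sugar ingested.** 1.8 × 80 = 144 g: 96 g glucose and 48 g fructose.

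**3. Apparent over true oxidation.** Let e_g and e_f be tracer mg per g of glucose and fructose, and f the fructose share of the exogenous carbohydrate oxidised. Breath label is proportional to (1 − f)·e_g + f·e_f. Dividing by e_g gives

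ratio = (1 − f) + f·(e_f/e_g).

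With oxidation in the ingested proportion, f = 1/3:

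| Assumed tracer, glucose + fructose | e_g (mg/g) | e_f (mg/g) | e_f/e_g | Ratio, Rexo = glucose |
|---|---|---|---|---|
| 200 + 200 mg | 2.083 | 4.167 | 2.00 | 1.333 |
| 100 + 100 mg | 1.042 | 2.083 | 2.00 | 1.333 |
| 133 + 67 mg (2:1) | 1.389 | 1.389 | 1.00 | 1.000 |
| 150 + 50 mg | 1.562 | 1.042 | 0.67 | 0.889 |
| 67 + 133 mg | 0.694 | 2.778 | 4.00 | 2.000 |

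Only the split matters for this ratio. Reading the amount as per serving (144/4 = 36 g each) raises every enrichment fourfold and leaves the ratio unchanged. With assumed natural abundances (sugars −10 to −26 per mil, resting breath −20 to −24 per mil), the equal-mass 1.333 moves only to about 1.29–1.36.

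**4. Equal masses, other oxidised shares.** With Rexo = glucose the ratio is 1 + f: 1.20 at f = 0.20 and 1.50 at f = 0.50. With Rexo = whole drink it is (1 + f)/(4/3): 0.90 at f = 0.20, 1.00 at f = 1/3, 1.125 at f = 0.50. Each gram of fructose still counts twice as much as a gram of glucose.

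**5. Illustration of level (assumed true exogenous 1.0 g/min, total 2.5 g/min, equal tracer masses, Rexo = glucose).** Exogenous reads 1.33. Taking efficiency as oxidised over ingested (the plan gives no formula for it), 1.0/1.8 = 56% reads 1.33/1.8 = 74%. Endogenous reads 2.5 − 1.33 = 1.17 instead of 1.50 g/min.

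**6. Between-arm contrast.** If f is the same in both arms, the factor is common. It cancels in the ratio of arms and leaves a paired test on exogenous oxidation unchanged. It does not cancel in the endogenous contrast, which becomes Δtotal − 1.33·Δexogenous. If f differs by arm (assumed values, equal tracer masses), the ratio of arms is distorted by 1.36/1.30 = 1.046 for 0.30 vs 0.36, and by 1.40/1.25 = 1.12 for 0.25 vs 0.40.

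**The case against.** A reader might infer that the trial will overstate exogenous oxidation by a third and over-weight fructose. The documents do not support that as a flat statement. It needs a literal glucose-only Rexo and equal tracer masses together, and neither is settled. A 2:1 tracer split is just as compatible with the text and gives no error of either kind.

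The literal reading of Rexo is itself open to doubt. B5.4 labels its total-carbohydrate equation as glucose oxidation, subtracts exogenous glucose from total carbohydrate, and defines Rref by both tracers. The word glucose may therefore be shorthand for the ingested carbohydrate. On that reading the average error is zero when the sugars are oxidised 2:1.

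A reader might also infer that the test of Hypothesis 2 is invalid. That does not follow either. The hypothesis is comparative, the same drink is planned in both crossover periods, and a constant factor drops out of the paired comparison of exogenous oxidation. In addition, the abstract's primary objective and the sample size concern microRNA, not this outcome.

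These arguments limit the size and severity of the point, but they do not remove it. The shorthand reading answers the divisor problem and leaves the weighting problem. No section requires equal enrichment or an assay of the drink.

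**Conclusion.** The point holds in conditional form. As worded, the divisor is correct for this drink only if both sugars carry equal enrichment, and the plan does not impose that condition. Under a literal Rexo with the sugars oxidised 2:1, the ratio of apparent to true exogenous oxidation is about 1.33 for equal tracer masses (1.29–1.36 with assumed natural abundances). It is 0.89, 1.00 or 2.00 for the other splits shown. Size and direction are therefore undetermined by the documents. Under a whole-drink Rexo the average error is zero at 2:1 oxidation, but equal tracer masses still weight fructose twofold.

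The quantities exposed are absolute exogenous oxidation, efficiency relative to dose, and endogenous oxidation. The between-arm contrast in exogenous oxidation is biased only if enrichment is unequal and the oxidised fructose share differs by arm: about 5% to 12% in the assumed examples. This should be fixed for Objective 2, but it is not a must-fix for the trial.

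**What to change.** - **B5.3, Carbohydrate Supplementation:** state the mass of each tracer and its basis (per serving, per bout or per volume). Apportion the two tracers in the drink's own 2:1 sugar ratio, so that both sugars carry equal enrichment. The carbohydrate dose is unchanged.
- **B5.4, Calculations of Exogenous and Endogenous Glucose Oxidation:** define Rexo as the measured isotopic enrichment of the mixed drink, from one aliquot per batch added to the existing isotope shipment. Label the result exogenous carbohydrate oxidation.

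The cost is a few sentences of protocol text, attention to how the tracers are weighed, and a few extra isotope assays, with no added participant procedure. If a 2:1 split and a whole-drink Rexo are already intended, only the wording and the aliquot are new. The tracer split must be settled before drinks are prepared, because unequal weighting cannot be corrected from the breath data.

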12 healthy, non-obese, recreational active male and female participants between the ages of 18-39. After a glycogen depletion protocol, volunteers will drink a carbohydrate (CHO: $1.0 \text{ g}\cdot\text{kg}^{-1}\cdot\text{hr}^{-1}$ body mass) or an energy free control (CON) beverage during the 3-hr post-exercise recovery phase to assess the initial phase of glycogen repletion on microRNA expression. For the remainder of the day participants will consume meals ready-to-eat (MRE) components designed to adequately ($6.0 \text{ g}\cdot\text{kg}^{-1}\cdot\text{d}^{-1}$ carbohydrate) or inadequately ($1.5 \text{ g}\cdot\text{kg}^{-1}\cdot\text{d}^{-1}$ carbohydrate) replenish glycogen stores. Volunteers will return to the laboratory the following day to assess how modified daily carbohydrate intake following glycogen depletion influences microRNA expression. At this time, volunteers will complete 80-min of steady-state ($60\% \text{ VO}_{2\text{peak}}$) cycle ergometry, while consuming carbohydrate at a rate of $1.8 \text{ g}\cdot\text{min}^{-1}$ to determine of how initiation of exercise with adequate or low glycogen stores effects exogenous carbohydrate efficiency. Following a minimum 7-d washout period participants will return to the laboratory to complete the second arm of the investigation. All testing will take place at the USARIEM research labs in Natick, MA.

B2. BACKGROUND AND SIGNIFICANCE

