
B3. MILITARY RELEVANCE

Military personnel often engage in sustained physical activity while time to eat and availability of food is limited (4, 36, 37). Under such conditions, it is likely that skeletal muscle glycogen stores are depleted, reducing the service member's ability to maintain an optimal level of physical performance. However, during 'real-world' military training operations there is limited knowledge regarding altered carbohydrate metabolism at the skeletal muscle level, as invasive investigations requiring muscle biopsies cannot be conducted during training operations. Identifying the mechanism, as well as determination of non-invasive markers of molecular pathways regulating carbohydrate metabolism is critical to move findings from controlled laboratory settings to field operations. Modeling of circulating microRNA may allow for a more comprehensive understanding of nutrient adequacy during military operations, allowing for implementation of targeted nutrition interventions to optimize military performance. Support for this protocol comes from Defense Health Program (DHP) Research funds, under Joint Program Committee-5 Nutrition and dietary supplements working group.

B4. OBJECTIVES/SPECIFIC AIMS/RESEARCH QUESTIONS

Objectives

1. Determine the influence of carbohydrate availability (e.g., glycogen depletion and repletion) on skeletal muscle microRNA expression, and if changes in circulating microRNA are reflective of changes in skeletal muscle microRNA.

1 2. Determine how initiation of exercise with adequate or low glycogen stores effects exogenous
2 carbohydrate efficiency.

3

4 **Hypotheses**

5

6 1. Expression of microRNA in skeletal muscle will be influenced by alterations in glycogen status, and
7 that these changes in skeletal muscle microRNA will be associated with modulation in circulating
8 microRNA.

9

10 2. Exogenous carbohydrate efficiency will be greater when exercise is initiated with lower glycogen
11 stores. Increased efficiency will be associated with higher phosphorylation of IRS-1 and AMPK.

12 **B5. RESEARCH PLAN**

13

14 **B5.1 Research Design**

15 This study will be a randomized cross-over placebo control trial.

16

17 **B5.2 Research Subjects/Population(s)**

18

19 **B5.2.1 Subject Population(s)**

20 Subject population will be representative of active duty male and female service members, being in good
21 health and recreationally active.

22

23 **B5.2.2 Number of Subjects, Records, and/or Specimens**

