41 amplified using index-tagged primers to facilitate multiplexing. The amplified cDNA constructs will be size-
42 selected, quality controlled before loading to the NextSeq instrument to generate 50 base reads. Image
43 analysis and base calling will be performed using the Illumina pipeline.

44

45 Preprocessing of raw base calls, sample de-multiplexing, trimming and filtering will be similar to that
46 described in 'Analysis of sequencing output'. For the miRNA quantification/enrichment, reads are first
47 aligned to the Rfam RNA database to filter and profile other small RNA species in the samples. Then reads
48 are mapped for small RNA annotation against reference zebrafish mature mature RNA sequences from the
49 miRBASE database. The miRNA read count matrix for each sample will be generated using open source
50 tools such as PICARD.

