Following identification of skeletal muscle microRNA that had a significant change, Taqman® probes (Applied Biosystems) will be used to assess the expression of these microRNA in serum to determine their potential use as noninvasive markers of altered carbohydrate metabolism following glycogen depletion and repletion. Total circulating miRNA will be extracted from 200 μ L serum using miRNeasy Serum/Plasma kit, which allows for extraction and purification of small (< 200 nt) cell-free RNA (Qiagen, Valencia, CA, USA). Exosomal circulating miRNA will also be extract from 1000 μ L serum using miRCURY™ RNA Isolation Kit to measure miRNA. To avoid introduction of potentially contaminating material, prior to RNA extraction serum samples will be centrifuged for 10 min at 4°C to remove cellular debris. Supernatant will be removed and transferred to a new tube without disturbing the pellet. Due to the small amount of RNA in the serum, 3.5 μ L of a Spike-In Control (C. elegans miR-39; Qiagen) will be added to all samples prior to extraction of RNA to determine the yield of template recovered. After extraction 3 μ L of serum RNA will be reverse transcribed using the TaqMan® microRNA RT kit (Applied Biosystems) with miRNA-specific stem-loop RT primers pooled in 1X-Tris-EDTA (TE) buffer for a final dilution of 0.05X. A pre-amplification step will be performed after reverse transcription to increase cDNA template using a primer pool of 20 X Taqman® Small RNA Assays (Applied Biosystems) for miRNA of interest at 0.05X concentration in 1X TE buffer. All serum miRNA will be normalized to the geometric of external (Spike-In Control C. elegans miR-39) and internal controls to allow for both technical and inter-individual normalization (47). Geometric mean of controls will be used to correct for possible outlying values and abundance differences between the different controls (48).

All reverse transcription for mRNA and miRNA, and pre-amplification of serum miRNA will be conducted in a T100™ Thermal Cycler (Bio-Rad, Hercules, CA). A StepOnePlus™ real-time PCR system (Applied Biosystems) will be used to perform all mRNA and miRNA analysis. Fold changes will be calculated using the $\Delta\Delta C_T$ method as described below in statistical analysis section.

Bioinformatics Analysis

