microRNA with significant changes in their expression will be uploaded to DNA Intelligent Analysis (DIANA)-miRPath 3.0 (Alexander Fleming Biological Sciences Research Center [BSRC], Athens, Greece; <http://diana.cslab.ece.ntua.gr>) to determine potential molecular pathways that these microRNA have previously been reported to regulate. Relevant Kyoto Encyclopedia of Genes and Genomes (KEGG; <http://www.genome.jp/kegg/>) pathways will be identified using experimentally verified targets from TarBase 7.0 (Alexander Fleming BSRC). Based on findings from this analysis, relevant gene and protein expression of relevant targets will be assessed.

Western Blotting

Approximately 30 mg of muscle will be homogenized in ice-cold buffer (1:10 wt/vol) containing 50 mM Tris-HCl (pH 7.5), 5 mM Na-pyrophosphate, 50 mM NaF, 1 mM EDTA, 1 mM EGTA, 10% glycerol (v/v), 1% Triton-X, 1 mM DTT, 1 mM benz-amidine, 1 mM PMSF, 10 μ g mL⁻¹ trypsin inhibitor and 2 μ g mL⁻¹ aprotinin. Homogenate will be centrifuged for 15 min at 10,000 \times g at 4°C. Protein concentration of supernatant (lysate) will be determined using 660 nm Protein Assay (ThermoFisher Scientific, Waltham, MA, USA). Phosphorylation status and total protein expression of molecular markers associated with carbohydrate metabolism will be determined using Western blot. Muscle lysates will be solubilized in Laemmli buffer, with equal amounts of total protein (15 μ g) separated by SDS-PAGE using precast Tris-HCl gels (Bio-Rad). Proteins will be transferred to polyvinylidene fluoride (PVDF) membranes and exposed to commercially available primary antibodies of intracellular markers involved with muscle metabolism to include but not limited to Akt, p-Akt^{Ser473}, AMPK α , p- AMPK α ^{Thr172}, PGC-1 α , SIRT1, ACC, p-ACC^{Ser79}, PDK4, IRS1, p-IRS1^{Ser302}, GSK-3 β , p-GSK-3 β ^{Ser9}, GSK-3 α , p-GSK-3 α ^{Ser21}, GLUT4 and PEPCK (Cell Signaling Technology, Danvers, MA, USA) at 4°C overnight. Labeling will be performed using secondary antibody (anti-rabbit IgG conjugate with horseradish peroxidase; Cell Signaling Technology), and chemiluminescent reagent will be applied (Super Signal, West Pico Kit; Pierce Biotechnology, Rockford, IL, USA). Blots will be quantified using a phosphoimager (ChemiDoc XRS; Bio-Rad) and Image

1 Lab software (Bio-Rad). To confirm equal protein loading per well a normalizing protein such as GAPDH or
2 β -actin will be assessed.
3

4 **Citrate Synthase Activity**

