5 Homogenate from muscle samples prepared for Western blotting will be used to assess citrate synthase
6 activity. Enzyme activity will be determined using a colorimetric assay analyzed on an SpectraMax® M
7 Series Multi-Mode Microplate Reader (Molecular Devices, Sunnyvale, CA, USA), by combining 10 μ l of
8 diluted (1:10; 0.1 M Tris HCl pH 8.1) sample to 150 μ l of reaction master mix (1 mL DNTB, 3 mg Acetyl
9 CoA, and 8 mL 0.1 M Tris HCl pH 8.1). The reaction was initiated when 10 μ l of 10 mM oxaloacetate was
10 added to each well (49). Samples were read at 412 nm. Data were normalized to protein content.
11

12 Any use of the data or samples outside of this defined research plan will be submitted as a protocol
13 amendment or a new protocol.
14

15 **B5.5 Managing Data and/or Human Biological Specimens for this Research**

16 All data and medical information obtained will be considered privileged and held in confidence. Study
17 volunteers will be assigned unique subject identification (ID) numbers that will not contain any personal
18 identifiers such as name, social security number, address, date of birth, zip code, etc. This study subject
19 ID number will be used on all data collection instruments, to include questionnaires, data collection
20 forms(**Appendix D-F**), computer records, etc. A number will be assigned as each volunteer is medically
21 cleared for participation. A master list linking the volunteers' names and ID numbers will be kept in a
22 separate locked file in the principal investigator's or project manager's office, or kept in a computer file with
23 password-protected access restricted to the principal investigator and project manager. When the results
24 of the research are published or discussed in conferences, no information will be included that would reveal
25 identity. De-identified muscle RNA samples for miR sequencing will be shipped USACEHR and breath
26 samples for isotopic analysis will be shipped to Metabolic Solutions via FedEx and stored in these
27 laboratories until analyzed. Once analyzed, there will be no remaining sample for storage. All other study
28 samples will be analyzed at USARIEM and stored in n -80°C freezer at USARIEM in room 322 or 304. All
29 samples will be stored using the subject identification number.
30

31 Only personnel assigned to the research study by the principal investigator will have access to the data.

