32 Hard copy data records will be stored for a minimum of three years from the time the study is completed.
33 Electronic data records will be maintained for a period of at least five years after the study has been
34 completed.
35

36 **B5.6 Managing Data and/or Human Biological Specimens for Future Research**

37 Any use of the samples outside of this defined protocol will be submitted as a protocol amendment or a
38 new protocol. Samples will be retained for future analyses once the protocol is closed if the subject
39 provided permission in the informed consent document.
40

41 **B5.8 Statistical Analysis**

42 **B5.8.1 Sample Size Estimation**

43 Statistical power and sample size were determined using the minimum fold change required for a
44 physiologically relevant difference in microRNA expression. Variance (standard deviation) was based
45 on recent publications assessing change in microRNA expression in skeletal muscle (18, 50, 51) and
46 circulating (34, 35, 52) in response to an acute bout of exercise. Using this information the sample
47 size necessary to determine statistical significance between intervention arms, with a mean fold
48

1 change of 1.5 ± 1 is 9 per group, with an alpha of 0.05 and 80% power. In the present study, 12
2 volunteers will be studied in a repeated measures crossover design to account for potential greater
3 inter-individual variability.
4

5 **B5.8.2 Data analysis**

7 Statistical analyses will be conducted using either SPSS (IBM Corp. Armonk, NY), SAS 9.3 (SAS
8 Institute Inc., Carey, NC), or equivalent. Common descriptive statistics will be used to describe
9 volunteer characteristics. Shapiro-Wilk tests will be used to determine normality of data. Mixed
10 model repeated measures ANOVA will be performed to determine main effects of time (baseline,
11 immediately, 3-hr, and 24-hr post glycogen depletion), carbohydrate intake ($6.0 \text{ g} \cdot \text{kg}^{-1} \cdot \text{d}^{-1}$ versus $1.5 \text{ g} \cdot \text{kg}^{-1} \cdot \text{d}^{-1}$) and time-by-carbohydrate interactions for skeletal muscle and circulating microRNA, mRNA
12 expression, and markers of nutritional status. If interactions are significant, Bonferroni correction will
13 be used to examine these relationships. Correlation coefficients and multiple regression analysis will
14 be used to evaluate relationships between study outcome measures. The alpha level will be adjusted

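### Small-RNA reads from human muscle are to be annotated against zebrafish microRNAs; followed as written, this would miss or mislabel some human microRNAs

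*Combined protocol and SAP*

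**What the plan says.** The B1 Abstract describes 12 "healthy, non-obese, recreational active male and female participants between the ages of 18-39". Section B5.3 (Muscle Biopsy) takes the tissue from the vastus lateralis, and microRNA expression is one of its stated uses. Section B5.5 adds: "De-identified muscle RNA samples for miR sequencing will be shipped USACEHR".

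Section B5.4 (mRNA and microRNA Expression) sets out the sequencing pipeline. Reads are first aligned to Rfam, to filter out and profile other kinds of small RNA. They then "are mapped for small RNA annotation against reference zebrafish mature mature RNA sequences from the" miRBase database, and a microRNA read count matrix is produced for each sample.

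Two later steps in B5.4 use the muscle results. The serum assays begin "Following identification of skeletal muscle microRNA that had a significant change", so the muscle findings decide what is measured in serum. Under Bioinformatics Analysis, "microRNA with significant changes in their expression will be uploaded to DNA Intelligent Analysis", and the pathways found there guide which gene and protein targets are examined next. Both steps serve Objective 1 in B4: "Determine the influence of carbohydrate availability (e.g., glycogen depletion and repletion) on skeletal muscle microRNA expression", and whether circulating microRNA reflects those changes.

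**The concern.** The reference determines which microRNAs can appear in the count matrix and what they are called. Here the samples are from one species and the reference is from another, and the protocol does not acknowledge the difference. A human microRNA with no zebrafish counterpart would either fail to map or be assigned to a related zebrafish entry.

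Sequencing is the only untargeted microRNA measurement described. A microRNA lost at that point would not be recovered by PCR on targets chosen afterwards. One counted under the wrong name could lead to the wrong serum probe or the wrong pathway query. What is at stake is the completeness and correct labelling of the muscle results on which Objective 1 depends.

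**Working it through.** The plan states no figure for this step that could be reproduced. The check is a comparison of the text, followed by a count of the libraries exposed.

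**1. Species of sample against species of reference**

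| Item | Stated | Where |
|---|---|---|
| Participants | Human adults aged 18–39 | B1 Abstract |
| Tissue | Vastus lateralis biopsy | B5.3, Muscle Biopsy |
| Material sent for sequencing | Muscle RNA | B5.5 |
| First alignment | Rfam, to filter and profile other small RNA | B5.4 |
| microRNA annotation | Zebrafish mature sequences, miRBase | B5.4 |
| Human microRNA reference | None named | – |
| Reason for zebrafish, or a second mapping | None given | – |

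The Rfam step does not fill the gap, because its described purpose is to deal with other RNA species before the microRNAs are annotated.

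**2. What follows if the text is applied literally**

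- Human sequence matches a zebrafish entry: the reads are counted.
- No matching zebrafish entry and no near match accepted: the reads are absent from the matrix.
- No matching zebrafish entry but a near match accepted: the reads are counted under another name.

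The split between these cases depends on the two sequence lists and on the number of mismatches allowed. The documents give neither, so no percentage can be derived.

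**3. Libraries exposed**

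Inputs: 12 volunteers with complete data (B5.2.2); two arms; ten biopsies per volunteer, five per arm (B5.3, Muscle Biopsy); four ANOVA time points, namely baseline and "immediately, 3-hr, and 24-hr post glycogen depletion" (B5.8.2).

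- If the four ANOVA time points are sequenced: 12 × 4 × 2 = 96 libraries.
- If every biopsy is sequenced: 12 × 10 = 120 libraries.
- The difference is the fifth biopsy: 12 × 1 × 2 = 24 libraries.

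The protocol does not say whether the fifth biopsy is sequenced; B5.3 (Study Design) assigns it to markers of glucose uptake and substrate use. Both totals cover completers only. B5.2.2 expects to consent 44 people to obtain 12 complete data sets, so any libraries from volunteers who stop early would be additional.

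**4. Direction of the effect on the comparison**

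The same reference applies to every sample in both arms of a crossover. Leaving a microRNA out removes it from both arms alike, so the omission does not in itself produce a difference between carbohydrate conditions.

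**The case against.** The strongest reply is that this is carried-over text and the laboratory will use a human reference as a matter of course. The repeated word in the sentence, and a nearby pointer to a description of sequencing-output analysis that is not in the supplied document, both fit that reading. It may be right, but the documents do not settle it. The sentence is complete and legible, it is the only mapping instruction given, and the sequencing is sent to a separate centre. It therefore needs correcting even if nobody intended it. What stands is that the harm is conditional on the text being followed.

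The second reply is that PCR carries the analysis. B5.4 says of the real-time PCR system that it "will be used to perform all mRNA and miRNA analysis", and B2 names several candidate microRNAs that PCR could measure without this reference. That limits the reach of the error: PCR results do not pass through the zebrafish mapping. It does not remove it. The protocol still describes sequencing and a read count matrix, it does not commit to the B2 candidates as the list to be measured, and it does not say which assay defines a significant change in muscle.

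Third, the effect on the microRNAs of interest is unknown and might be small. This stands, and no share is claimed. The library counts show how widely the rule applies, not how many microRNAs are lost. Objective 2, on exogenous carbohydrate efficiency, does not depend on this step.

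**Conclusion.** The point holds: the stated annotation reference is the wrong species for the samples, and nothing elsewhere in the document corrects or explains it. If followed as written, it applies to all sequenced muscle libraries, 96 or 120 among completers depending on the fifth biopsy. Some human microRNAs would then be missed or mislabelled, in a proportion the documents do not allow one to estimate.

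The conclusion about the text is firm. The consequence rests on two assumptions: that the pipeline is run literally, and that some human microRNAs present in muscle lack a matching zebrafish sequence. The damage would be lost or misdirected findings under Objective 1, and through them the serum and pathway work; no bias in the carbohydrate comparison is shown. Because the step feeds the primary objective and the correction is cheap, it should be made before the sequencing results are used.

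**What to change.** In B5.4, replace the zebrafish reference with human (*Homo sapiens*) mature sequences and state the miRBase release. Confirm with the sequencing laboratory which reference was actually used. If it was human, the text correction is enough. If it was zebrafish, re-map the affected libraries from the raw reads before serum targets are chosen or pathway analysis is run.

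Three clarifications belong in the same edit:

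- supply the trimming and filtering steps in place of the pointer that leads nowhere in the supplied text;
- state the number of mismatches allowed;
- say whether sequencing or PCR defines a significant change in muscle.

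The reference correction is one line. Re-mapping needs computing time only, with no new volunteers, visits or biopsies. If serum targets have already been selected from zebrafish-mapped counts, the selection should be repeated, and further assays on stored serum might be needed.
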